**Bronchodilator (albuterol):**

This medication will be available to be administered for post-bronchodilator testing or if the participant is uncomfortable from the effects of the methacholine challenge test. Albuterol can lead to tremor, nervousness, tachycardia, palpitations and headache – these reactions are transient and rare (<5%) with the proposed doses used for this study, and if they occur, we will monitor the patient until they return to baseline. High doses may cause arrhythmias and hypokalemia: these are very unlikely with the doses used for this study.

**Exhaled breath condensate:**

This involves breathing out into a refrigerated container – there are no risks involved.

**Exhaled nitric oxide:**

There are no risks to this procedure other than possible light-headedness if the participant breathes out too hard during exhalation.

**Forced Oscillation:**

This will be performed in conjunction with the methacholine testing and induced sputum procedure. There are no risks involved in this test. Some subjects may feel discomfort from the slight oscillation of air in their mouth while they breathe. This technique has been used safely in many studies, including those involving infants.

**Induced Sputum:**

This involves inhaling hypertonic saline which, may induce bronchoconstriction, and so we will administer albuterol prior, and monitor lung function during, but is generally well tolerated.

**Methacholine challenge:**

This test involves the inhalation of an agonist to induce bronchoconstriction and may induce the symptoms of asthma (chest tightness, dyspnea, coughing). The procedure is performed in a closely monitored clinical environment, with availability of bronchodilator. This procedure has been safely used in many previous studies in our division and nationwide. We will only perform this procedure if the baseline FEV1 is  $\geq$  60% predicted and  $\geq$  1.5 Liters (which is one of the eligibility criterion for the MIMDA study). We will not perform if participants have uncontrolled hypertension (SBP  $>$  200 or DBP  $>$  100), known aortic aneurysm, history of heart attack or stroke in the last 3 months or current use of cholinesterase inhibitor for myasthenia gravis.

**MitoQ:**

This over the counter supplement is usually well tolerated. In previous studies the main side effect noted has been mild nausea (incidence 15% with 40 mg dose being proposed for this study), which appears dose related, and is most significant at doses of 80 mg per day and above.

**Nasal Brush (Nasal epithelial cell isolation):**

These are collected by scraping the back of the nose. This may cause a slight tickling sensation. On rare occasions (approx. 1%) it could cause some minor nasal bleeding, which is self-limited.

**Nasal Strip:**

We will place a small strip into the back of the nose and ask the participant to hold it in place against the inside of their nasal cavity to collect surface lining fluid. The participant will need to breathe through their mouth while their nose is pinched shut, which they may find uncomfortable. This process will take approximately 1 minute. They may experience a mild discomfort, runny nose, or sneezing when the nasal strips are placed in their nose. There is a very small risk that you could experience a nose bleed.

**Nasal Lavage:**

There are no known risks associated with this procedure.

**Spirometry:**

This is a standard clinical test that may cause discomfort by breathing forcefully through a mouthpiece while wearing nose clips. Occasionally some subjects may feel lightheaded. All testing is done in a seated position under direct monitoring.

**Lung volumes (Plethysmography):**

This is a standard clinical test with no known risks. Participants may experience discomfort from sitting briefly in a confined space of clear Plexiglas the size of a phone booth, and breathing through a mouthpiece that is briefly occluded for 1-2 seconds during measurement of thoracic gas volume. The mouthpiece occlusion may be interrupted at any moment by a signal from the participant and the door of the body plethysmograph can be opened at any time as well.

**Venipuncture:**

We will draw 30 cc of blood at every visit except 5b, which does not involve a blood draw. This will be a total of 150 cc total over 12 weeks. The main risks of venipuncture are discomfort and bruising.

**Urine:**

We will collect approximately 5 cc of urine at every visit. There are no known risks with urine collection.

**Confidentiality:**

The study includes a risk of loss of confidentiality. We will follow Health Insurance Portability and Accountability Act guidelines on confidentiality and minimize these risks by assigning unique identifiers to health information, maintaining all records in a locked storage area, and using password protected electronic devices. Blood will be stored for genotyping only with specific patient consent.

***Therapeutic Alternatives:*** List the therapeutic alternatives that are reasonably available that may be of benefit to the potential subject and include in the consent form as well.

**Not Applicable**

Participants will stay on their usual asthma medications per their asthma care provider. There are no medications specifically targeting obese patients with asthma. The alternative is not to participate in this study.

***Data Safety and Monitoring:*** The specific design of a Data and Safety Monitoring Plan (DSMP) for a protocol may vary extensively depending on the potential risks, size, and complexity of the research study. For a minimal risk study, a DSMP could be as simple as a description of the Principal Investigator's plan for monitoring the data and performance of safety reviews or it could be as complex as the initiation of an external, independent Data Safety and Monitoring Board (DSMB). The UVM/UVM Medical Center process for review of adverse events should be included in the DSMP.

The DSMB will include 3 physician scientists (not from the University of Vermont or Duke University) who are active in asthma research.

An adverse event (AE) is any unanticipated or unintended medical occurrence or worsening of a sign or symptom (including any clinically significant abnormal laboratory finding as determined by the study physician) or disease in a study participant, which does not necessarily have a causal relationship with the study condition, procedures or study agent(s), that occurs after the informed consent is obtained.

Pre-existing conditions or illnesses which are expected to exacerbate or worsen are not considered adverse events.

*Definition of a Serious Adverse Event (SAE)*

Serious Adverse Event (SAE): A Serious Adverse Event is defined as an AE meeting one of the following outcomes:

- Death during the period of protocol defined surveillance
- Life Threatening Event (defined as a participant at immediate risk of death at the time of the event)
- Inpatient hospitalization or prolongation of existing hospitalization during the period of protocol defined

surveillance

- Results in congenital anomaly or birth defect
- Results in a persistent or significant disability/incapacity

Any other important medical event that may not result in one of the above outcomes, may be considered a serious adverse experience when, based upon appropriate medical judgment, the event may jeopardize the participant and may require medical or surgical intervention to prevent one of the outcomes listed above

### **AE/SAE Grading and Relationship Assignment**

#### *Intensity (severity) Scale*

Each adverse event will be assessed by the site investigator for severity and classified into one the categories below:

- **Grade 1 (Mild):** event requires minimal or no treatment and do not interfere with the patient's daily activities.
- **Grade 2 (Moderate):** event results in a low level of inconvenience or concern with the therapeutic measures. Moderate events may cause some interference with functioning.
- **Grade 3 (Severe):** event interrupts a patient's usual daily activity and may require systemic drug therapy or other treatment. Severe events are usually incapacitating.
- **Grade 4 (Life threatening):** Any adverse drug experience that places the patient or participant, in the view of the investigator, at immediate risk of death from the reaction as it occurred, i.e., it does not include a reaction that had it occurred in a more severe form, might have caused death.
- **Grade 5 (Death)**

#### **Relationship Assessment**

For all collected AEs, the site investigator who examines and evaluates the subject will determine the adverse event's causality based on temporal relationship and his/her clinical judgment. The degree of certainty about causality will be graded using the categories below:

- **Definitely Related:** There is clear evidence to suggest a causal relationship, and other possible contributing factors can be ruled out. The clinical event, including an abnormal laboratory test result, occurs in a plausible time relationship to study visit.
- **Probably Related:** There is evidence to suggest a causal relationship, and the influence of other factors is unlikely. The clinical event, including an abnormal laboratory test result, occurs within a reasonable time sequence to administration of the study visit, is unlikely to be attributed to concurrent disease or other drugs or chemicals.
- **Possibly Related:** There is some evidence to suggest a causal relationship. However, the influence of other factors may have contributed to the event (e.g., the subject's clinical condition, other concomitant events).
- **Unlikely:** A clinical event, including an abnormal laboratory test result, whose temporal relationship to study visit makes a causal relationship improbable (e.g., the event did not occur within a reasonable time) and in which other drugs or chemicals or underlying disease provides plausible explanations (e.g., the subject's clinical condition, other concomitant treatments).
- **Unrelated:** The AE is completely independent of study, and/or evidence exists that the event is definitely related to another etiology. There must be an alternative, definitive etiology documented by the clinician.
- **Expected Events Related to Disease Process:** Expectedness refers to the awareness of adverse events related to study.

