### **1. Serious Adverse Events**

The protocol will be stopped for two serious adverse events that are definitely or probably related to the study protocol. The protocol will be stopped in the event that there are three events that are thought to be possibly related to the study protocol.

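### Three adverse event causality grades are timed against the study visit instead of the daily study drug, so a drug-caused event between visits can be graded too low for the stopping rules

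*Combined protocol and SAP*

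**What the plan says.** Under Relationship Assessment, the site investigator "will determine the adverse event's causality based on temporal relationship and his/her clinical judgment". Six categories follow, and three of them name what the timing is measured against:

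- Definitely Related: the event "occurs in a plausible time relationship to study visit".
- Probably Related: the event "occurs within a reasonable time sequence to administration of the study visit".
- Unlikely: an event "whose temporal relationship to study visit makes a causal relationship improbable", with a second condition: "and in which other drugs or chemicals or underlying disease provides plausible explanations".

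Possibly Related has no timing clause: "There is some evidence to suggest a causal relationship. However, the influence of other factors may have contributed to the event". Unrelated and the category for expected events have none either. No category mentions the study drug or a dose.

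These grades feed two sets of rules. Under Reporting, the 48-hour reports for grade 3 and grade 4 events require at least Possibly. Under Stopping rules, the serious adverse event rule reads "The protocol will be stopped for two serious adverse events that are definitely or probably related to the study protocol", and then sets a limit of three for possibly related events. The rule for non-serious events stops the protocol at four grade 3 events, counting only those definitely or probably related.

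**The concern.** The trial tests a supplement taken every day (Rationale for dose of active supplement), and its Toxicity text lists gastrointestinal effects that exceed placebo: nausea 31.2% against 17.1%, and vomiting 14.6% against 4.9%, at 40 mg per day. Effects of this kind follow dosing. A clinic visit is the right reference point for harm from a visit procedure such as the methacholine challenge or sputum induction. It is the wrong one for harm from the drug.

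The adverse event definition covers both study agents and procedures, and the next section, Study Drug Action Taken, speaks of study drug administration. Relationship Assessment is therefore out of line with the text on either side of it. At stake is whether drug-caused events reach the categories that prompt expedited reports and count toward stopping the trial.

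**Working it through.** The plan states no figure on this point, so the check sets the definitions against the rules that use them. A numerical illustration follows, for scale only.

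**Step 1. Gap between dosing and visits.** From the Outline of Study Visits, nominal days counted from randomization, ignoring visit windows:

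- V2 is day 0, V3 is day 14, V4 is day 42 and V5b is day 84. V5a is 1 to 10 days before V5b, so day 74 to 83.
- V2 to V3: 14 days. V3 to V4: 42 − 14 = 28 days. V4 to V5a: 74 − 42 = 32 to 83 − 42 = 41 days.
- The phone call at about day 3 carries no visit number.

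Dosing is daily, so an event can follow a dose closely and still be weeks from any visit.

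**Step 2. Grade a drug-caused event remote from any visit, taking each definition literally.**

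| Category | Timing clause | No plausible alternative cause | Plausible alternative cause |
|---|---|---|---|
| Definitely | study visit | fails on timing | fails on timing and on ruling out other factors |
| Probably | study visit | fails on timing | fails on timing |
| Possibly | none | available | available |
| Unlikely | study visit, plus an alternative cause | fails on the second condition | available |
| Unrelated | none | not available | needs a documented, definitive other cause |

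The highest grade open to the event is Possibly. Where another explanation is plausible, Unlikely is open too. In poorly controlled asthma with controller treatment, such an explanation will often be at hand.

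**Step 3. Follow each grade into the rules.**

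| Grade given | 48-hour report (grade 3 or 4) | Serious event stop | Grade 3 non-serious stop |
|---|---|---|---|
| Definitely or Probably | yes | counts toward 2 | counts toward 4 |
| Possibly | yes | counts toward 3 | does not count |
| Unlikely | no | does not count | does not count |

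An event graded Unlikely reaches oversight only through the 15-day report, which is at the investigator's discretion, or the annual summary of all adverse events.

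**Step 4. Illustration of scale.** Assumptions that are not in the documents: 20 participants on active drug (half of 40), at most one event each, true risk p of a drug-related event, and a share f of those events graded below Probably. Events on placebo are ignored. The chance of reaching a limit of k events is P(X ≥ k), with X binomial(20, p(1 − f)).

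Four-event grade 3 rule:

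| p | f = 0 | f = 25% | f = 50% |
|---|---|---|---|
| 0.10 | 0.133 | 0.058 | 0.016 |
| 0.20 | 0.589 | 0.352 | 0.133 |
| 0.30 | 0.893 | 0.690 | 0.352 |

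Serious event rule at p = 0.10, if every such event drops from Probably to Possibly: the chance of at least 2 events is 0.608. The chance of exactly 2 is 190 × 0.1² × 0.9¹⁸ = 190 × 0.01 × 0.1501 = 0.285. The chance of at least 3 is therefore 0.608 − 0.285 = 0.323.

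**The case against.** The best defence is that the investigator is not bound to the visit. The opening sentence of Relationship Assessment relies on timing, with no reference point named, and on clinical judgment. The adverse event definition names study agents, each event needs a study drug action to be classified, and the reporting and stopping rules speak of relation to the study or the study protocol, which can be read to include the drug. A sensible investigator would consider the drug. This is a fair account of what may happen in practice, but doing so means departing from the written definitions of Definitely and Probably, and two sites may not depart in the same way.

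Several stronger readings are tempting and are not supported:

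- A reader might infer that any event between visits simply belongs in Unlikely. It does not: that category also needs a plausible alternative explanation, and without one the event falls to Possibly.
- A reader might infer that such events escape reporting. Possibly still triggers both 48-hour reports and counts toward the three-event serious stop, and the annual summary covers all adverse events.
- A reader might count the dosing days lying outside some window after each visit and treat that share as the harm missed. The protocol sets no window, and a share of days is not a share of misgraded events.
- A reader might take the odd phrase about administering a visit as proof that a drug term was replaced. That is a reasonable guess about the drafting, not something the document states.

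**Conclusion.** The point holds in a limited form: the timing clauses of three categories are wrong as written. Their effect on Definitely and Probably is direct. Read literally, a drug-caused event remote from a visit cannot reach either grade, so it is lost to the four-event grade 3 rule and, if serious, is counted against three and not two. The effect through Unlikely is conditional on a plausible alternative cause; where it occurs, the event is lost to the 48-hour reports and to both stopping rules, though not to the annual summary.

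The documents give no expected rate of related grade 3 or serious events and no evidence on how investigators apply the definitions. They therefore show that drug-related harm can be undercounted, not that it systematically will be. The probabilities above show how sensitive the stopping rules are to misgrading; they do not estimate its frequency. Part of the Data Safety and Monitoring section just before the adverse event definition was not in the text reviewed, so any offsetting provision there could not be weighed.

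**What to change.** In Definitely, Probably and Unlikely, replace the reference to the study visit, including the phrase about administering it, with *study drug administration or study procedure*. The other categories carry no timing clause and need no edit on this point.

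In Reporting and in both stopping rules, state that relation to the study or the study protocol covers the study drug and the study procedures alike. Leave every reporting deadline and every stopping threshold as it is.

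The cost is wording in the protocol and the adverse event form. Sample size, visits and analysis are unaffected.

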### **Reporting**

Adverse event reporting for this protocol will be as follows:

- The PI's will submit a completed serious adverse event report to the IRB, NIH and Chair of the DSMP within 48 hours after any potentially life-threatening (grade 4) serious adverse event that is possibly, probably or definitely related to the study.
- The PI's will submit a completed serious adverse event report to the IRB, NIH and Chair of the DSMP within 48 hours after becoming aware of any Grade 3 (severe) adverse event that is possibly, probably or definitely related to the study.
- The PI's will report within 15 days on any other event or condition regardless of grade, which in their judgment represents an event reportable to the IRB, NIH and DSMP.
- A summary of all adverse events will be reported to the DSMP, NIH and IRB annually.

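### The causality scale includes an expectedness category that carries no relatedness grade, so an asthma event that is possibly study-related may miss 48-hour reporting and the three-event stopping count

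*Combined protocol and SAP*

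**What the plan says.** Under Relationship Assessment, the site investigator determines causality for every collected adverse event, and "The degree of certainty about causality will be graded using the categories below". Six entries follow at the same level: Definitely Related, Probably Related, Possibly Related, Unlikely, Unrelated, and "Expected Events Related to Disease Process". The whole definition of the last is "Expectedness refers to the awareness of adverse events related to study".

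The rules that use the grade are these:

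- **Reporting, 48 hours, grade 4.** A report is due "within 48 hours after any potentially life-threatening (grade 4) serious adverse event that is possibly, probably or definitely related to the study".
- **Reporting, 48 hours, grade 3.** A report is due for "any Grade 3 (severe) adverse event that is possibly, probably or definitely related to the study".
- **Reporting, other routes.** Within 15 days the principal investigators report "any other event or condition regardless of grade, which in their judgment represents an event reportable to the IRB, NIH and DSMP". All adverse events are also summarised once a year. Neither route needs a relatedness grade.
- **Stopping rules, 1. Serious Adverse Events.** "The protocol will be stopped for two serious adverse events that are definitely or probably related to the study protocol". A second sentence stops the protocol at three events thought possibly related.
- **Stopping rules, 2. Adverse Events.** The protocol stops at four non-serious grade 3 events judged definitely or probably related.

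**The concern.** Causality and expectedness are different attributes, and an event can be both expected and caused by the study. Placing expectedness on the causality list offers the investigator a code that answers a different question. The entry also does not fit its own label: the label refers to the disease, the definition to the study. From the text alone an investigator cannot tell whether an event given this code is related.

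The overlap is a real one in this trial. Participants are enrolled with poorly controlled asthma. They undergo sputum induction at visits 1 and 5a and methacholine challenge at visits 2 and 5b, and the schedule's own footnote says that both procedures can narrow the airways. Worsening asthma can therefore come from the disease, from the study, or from both. At stake is whether two sites would code the same event alike, and whether an event that should prompt an expedited report or count toward stopping does so.

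**Working it through.** No power, sample-size or event-rate figure is involved. The check sets each causality code against the rules that use it, then asks which events could move between codes.

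**Step 1. Which rules can each code satisfy?** There are two 48-hour conditions (grade 4 SAE; grade 3 event) and three stopping triggers (two SAEs; three possibly related events; four non-serious grade 3 events). Each rule is read literally.

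| Code | 48-hour conditions (of 2) | Two SAEs | Three possibly related | Four grade 3 | Stopping triggers (of 3) |
|---|---|---|---|---|---|
| Definitely | 2 | yes | no | yes | 2 |
| Probably | 2 | yes | no | yes | 2 |
| Possibly | 2 | no | yes | no | 1 |
| Unlikely | 0 | no | no | no | 0 |
| Unrelated | 0 | no | no | no | 0 |
| Sixth entry alone | 0 | no | no | no | 0 |

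An event that carries only the sixth code meets none of the five rules, whatever its severity.

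**Step 2. Which events could plausibly move to the sixth entry?** The scale's own definitions decide this.

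- *Definitely Related* requires that competing contributors have been excluded. *Probably Related* requires that concurrent disease be an improbable explanation. An investigator who has reached either judgment has little reason to choose a disease-process code.
- *Possibly Related* expressly allows the participant's clinical condition to have contributed. An exacerbation with mixed causes fits both this grade and the sixth entry, and no rule says which to use.
- *Unlikely* and *Unrelated* satisfy none of the five rules, so moving an event from either one changes nothing.

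The exposed group is therefore the events that would otherwise be graded Possibly Related.

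**Step 3. What changes for that group?** Moving from Possibly Related to the sixth entry takes the 48-hour conditions from 2 of 2 to 0 of 2, and the stopping triggers from 1 of 3 to 0 of 3. The one trigger lost is the three-event count. If n events would be graded Possibly Related and k of them are coded only in the sixth entry, the count is n − k, and the trigger is missed when n is at least 3 and n − k is below 3. With n = 3 and k = 1 the count is 3 − 1 = 2, one short. With n = 4, two events would have to move (4 − 2 = 2). The documents give no rate for such events, so no probability can be attached.

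**The case against.** The strongest reply is that the consequence is inferred. The severity scale tells the investigator to place each event in one category, whereas Relationship Assessment has no such wording. It asks for a degree of certainty about causality for every event, and the sixth entry supplies none. It could thus be an added descriptor, used together with one of the five grades. This stands in part: single choice is not stated. But one list of categories at one level is naturally read as alternatives, and nothing in the available text says that an event given the sixth code must also be graded.

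A second reply is that other safeguards remain. The 15-day judgment route, the annual summary, the external monitoring board and individual discontinuation need no relatedness grade. A reader might infer that events in the sixth category go unreported; the documents do not support that. These routes limit the harm, but none replaces a 48-hour report or feeds the stopping counts.

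A third is that the adverse event definition already leaves out expected worsening of a pre-existing condition, so some of these events never reach the causality scale. That is true, and it is a separate gap further upstream. Closing it would bring more asthma events to the scale, where the sixth entry awaits them.

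A reaction during a monitored challenge is a weak example, because it is readily attributed to the procedure. The ambiguity matters most for worsening with mixed causes.

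**Conclusion.** The causality scale is defective in a limited way. If its entries are alternatives, an asthma event with both disease and study as possible contributors may be left without a relatedness grade. It would then fall outside both 48-hour conditions and outside the three-event count.

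A reader might infer that the sixth entry disables all the stopping rules, including the two-SAE and four-event triggers. The documents do not support this: both of those need Definitely or Probably Related, and the definitions of these grades already make disease an improbable or excluded cause. Nor is it certain that any event will be lost, since that depends on how sites code and, for stopping, on a count that would otherwise reach three.

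The conclusion rests on reading the list as alternatives and on the text available. A stretch of text just before the adverse event definition was not available, and nothing is inferred from its absence. The point concerns safety oversight and leaves the primary analysis untouched.

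**What to change.** Remove the sixth entry from the causality list in Relationship Assessment, and record expectedness and relation to the underlying disease in a separate field on the adverse event form. Suitable wording would be: *Every recorded adverse event receives exactly one of the five relatedness grades. Expectedness and relation to underlying asthma are recorded separately and do not replace that grade.*

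Little information is lost, because Possibly Related, Unlikely and Unrelated already accommodate underlying disease or another cause, and the new field keeps the disease label. The exclusion of expected worsening in the adverse event definition should be reconciled with the scale in the same amendment.

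No threshold, reporting time or clinical rule changes. The cost is one protocol line and one form field.
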